## 1. INTRODUCTION

Intravascular imaging provides clinicians with information essential to the development of treatment strategy and avoidance of procedure-associated injuries to the vessel walls. Two primary modalities of such imaging are intravascular ultrasound (IVUS) and optical coherence tomography (OCT). Both have advantages and challenges for use in assessing occlusions and structures in peripheral arteries.

As the name denotes, IVUS uses high-frequency sound waves that rebound off vessel walls and are collected by a processing system. The intensity of the waves vary depending on the tissue encountered and the system electronics process those signals to create a cross-sectional image. It is used to measure plaque extent, morphology and distribution, but has low resolution and calcium deposits in the vessel walls can reduce penetration of the sound waves. OCT imaging uses near-infrared light to optimize intravascular visualization of tissue. OCT images have higher resolution and faster imaging acquisition than IVUS, but imaging requires management of blood flow, which can interfere with light transmission.

## 2. DEVICE AND TECHNOLOGY DESCRIPTION

[figure not shown]
The devices that will be used in this study are the Pantheris (Avinger, Inc.) and the Visions (Royal Philips Corp.) catheters. Both devices have been reviewed by the United States's Food and Drug Administration (FDA) and have marketing clearance for commercial use and use in diagnostic imaging in peripheral vessels. Neither device is considered investigational or experimental and in this study they will be used in accordance with their FDA-cleared indications for use.

### 2.1. Pantheris System and Catheter

[figure not shown]
The Pantheris system is comprised of the Pantheris catheter (Figure 1), Lightbox Imaging Sled (Sled), and the Lightbox HS Imaging Console (Lightbox). The catheter is connected to the Lightbox via the Sled and it is the Lightbox Console that displays the OCT images captured by the catheter's rotating laser. The Sled provides optical and rotational power to the Pantheris catheter.

The Pantheris catheter is a monorail (rapid exchange) device with a working length of 110 cm and is compatible with a 0.014" guidewire. The Pantheris is designed for treatment of lesions in vessels with a diameter of 3 mm to 7 mm. The catheter is provided sterile and is for single use only.

OCT imaging can differentiate neointimal morphology and its capability of determining stent malapposition, tissue protrusion around and through stent structure, and stent edge dissection allows the clinician to make decisions about treatment strategy (Figure 2). The system also has the capability to measure the diameter of the lumen of the vessel.

[figure not shown]
**FIGURE 1: PANTHERIS SYSTEM ELEMENTS; THE CATHETER (TOP), THE SLED (LOWER LEFT) AND THE LIGHTBOX (LOWER RIGHT).**

[figure not shown]
**FIGURE 2: VESSEL ANATOMY VISIBLE WITH OCT IMAGING BY THE PANTHERIS CATHETER.**

## **2.2. VISIONS IVUS catheter**

The Visions PV 0.014P IVUS catheter (Visions catheter) has a working length of 150 cm and is advanced through an indwelling vascular sheath, following an 0.014” guide wire. The catheter is connected with an imaging system that displays the images (Figure 3). The IVUS catheter permits the clinician to assess disease markers, such as plaque burden and lesion location and morphology, as well as provide measurements of the lumen of the vessel. It is provided sterile and for single use only.

**FIGURE 3: THE VISIONS IVUS IMAGING SYSTEM AND CONSOLE (A), AND VISIONS IVUS CATHETER (B).**

**FIGURE 4: VESSEL MORPHOLOGY AS IMAGED BY AN IVUS CATHETER.**

### **3. RISK/BENEFIT ASSESSMENT**

#### **3.1. Risks**

Introduction of either the Pantheris or Visions catheter into a peripheral artery carries some known risks.

Adverse effects possible with the use of the Pantheris OCT and Visions IVUS catheters include, but are not limited to, the following events:

- Vessel dissection, perforation, rupture or injury;
- Restenosis;
- Hemorrhage or hematoma;
- Infection;
- Vessel spasm;
- Embolism;
- Entry puncture site bleeding;
- Vessel thrombosis;
- Renal failure;
- Vessel trauma requiring surgical repair or intervention; and
- Death.

The patients involve in this study diagnostic imaging and the possible risks for diagnostic include, but are not limited to, the following events:

- Entry site complications
- Entry site pain
- Acute vessel closure
- Arterial rupture
- Arterial spasm
- Bleeding complications
- Infection

There are risks associated with the use of medical equipment connected to an energy source. These risks have been mitigated through in-house testing and compliance.

Risk will be mitigated by working with an Investigator who is experienced and skilled in endovascular diagnostic techniques. Additionally, only Investigators with experience of proper device operation will participate in this study.

#### **3.2. Benefits**

Knowledge gained in this study on the use of OCT or IVUS systems to assist in diagnosis and treatment planning may provide physicians with an additional option that is as good or better than what is available currently for visualization of vessel morphology during the procedure.

## **4. CURRENT INDICATIONS FOR USE FOR THE TWO DEVICES**

### **4.1. Pantheris System's Current Indications for Use**

The Pantheris System's OCT imaging system being used in this study was originally cleared under K152275 in October of 2015, with device iterations being reviewed in subsequent regulatory submissions. The device has been commercially available since 2016.

The Indications for Use statement for the Pantheris system is:

“The Pantheris System is intended to remove plaque (atherectomy) from partially occluded vessels in the peripheral vasculature with a reference diameter of 3.0 mm to 7.0 mm, using OCT-assisted orientation and imaging. The system is an adjunct to fluoroscopy by providing images of vessel lumen, wall structures and vessel morphologies. The Pantheris System is NOT intended for use in the iliac, coronary, cerebral, renal or carotid vasculature.”

The Pantheris catheter was cleared for diagnostic use under K162326.

### **4.2. VISIONS PV 0.014P's Current Indications for Use**

The Visions 0.014P device being used in this study was originally cleared by the FDA under K152829 in November 2015. The device is available commercially.

The Indications for Use statement for the Visions PV 0.014 IVUS catheter system is:

“The Visions PV 0.014 IVUS catheter is designed for use in the evaluation of vascular morphology in blood vessels of the coronary and peripheral vasculature by providing a cross-sectional image of such vessels. This device is not currently indicated for use in cerebral vessels. It is designed for use as an adjunct to conventional angiographic procedures to provide an image of the vessel lumen and wall structures.”

## **5. INVESTIGATIONAL PLAN**

### **5.1. Study Design Overview**

The purpose of this is a study to collect images of the same vessel segments using both the IVUS and OCT systems so that a comparison can be made of the two imaging modalities. IVUS and OCT images will be captured at identical positions within vessel segments. Continuous imaging will occur as the catheters are moved from distal to proximal endpoints established with a radiopaque marking tape attached to the subject's leg.

The trial will enroll up to 25 subjects diagnosed with peripheral arterial disease of the lower extremities, with the goal to acquire at least 115 matched images for analysis.

The images will be anonymized and given a unique identification prior to assessment by three radiologists (readers) for review. The readers will review the images and rank each for image clarity (using a visual analogue scale or VAS) and identification of vessel morphology and disease pre- and post-procedure.

The inclusion criteria for subjects are:

1. Subject is an adult ( $\geq 18$  years old); and
2. With suspected vascular disease that might be a candidate for IVUS; and
3. Reference vessel lumen is acceptable for use of the Pantheris and IVUS catheters as per visual angiographic estimation.
4. Successful diagnostic imaging and removal of the IVUS catheter with no adverse events.

The exclusion criteria are:

1. Subject, if female, is pregnant or breast feeding; or
2. Subject is unwilling to give informed consent.

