#### **5.4. Enrollment and Study Duration**

Subjects will be enrolled at 3 clinical sites in the USA.

Subjects will be considered enrolled into the study once the consent form is signed and the Pantheris catheter is introduced into the vasculature. Subjects will be considered exited from the study once the Pantheris catheter (OCT device) diagnostic imaging and vessel measurements have been completed. Enrollment is expected to start in Q1 2018, and conclude by the end of Q2 2018.

Subjects may withdraw at any time from the study without prejudice or detriment to their medical care. If a subject prematurely terminates from the study, the reason for the termination will be recorded. Subjects who actively withdraw from the trial will be considered “withdrawals.” If termination is a result of an adverse event or death, an Adverse Event Case Report Form will also be completed.

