#### **5.5. Duration of Subject Participation**

Participation lasts the duration of the diagnostic imaging procedure. No follow-up imaging or patient data will be collected.

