### **6. STUDY PROCEDURE**

#### **6.1 Gathering OCT and IVUS Images**

After providing informed consent, the subject will be prepared for the diagnostic procedure according to the institution’s and investigator’s standard procedures. Demographic information will be recorded for each subject.

A radiopaque ruler will be attached to the subject’s leg to provide reference marks for starting and stopping points of the “target segment” that will be used for image acquisition by the two devices.

Subjects will undergo diagnostic angiographic images to identify the target segment starting point (distal end) and ending point (proximal end) which will be between 5 cm and 10 cm within the vessel.

A 7 Fr vascular sheath will be advanced up-and-over the aortic bifurcation and to the region of interest of the artery.

A 0.014 inch guide wire will be advanced distal to the target segment under angiographic imaging.

An IVUS catheter will be loaded onto the wire and advanced until its imaging transducer resides at the distal end of the target segment (starting point). Using the radiopaque ruler as a reference of the starting point (distal end) and stopping point (proximal end) of the target segment, the IVUS catheter will be energized for imaging and retracted through the target segment (between 5 cm and 10 cm within the vessel) capturing images within the target segment.

The diameter of the lumen of the vessel at the starting, mid, and ending points of the target segment will be measured using the IVUS system software. Mean diameter and luminal area will be calculated for each target segment imaged.

After all images and measurements of the target segment have been captured on the IVUS system, the IVUS catheter will be removed.

Using the radiopaque ruler as a reference, an OCT catheter will be advanced over the 0.014 guide wire until its imaging window is at the exact same starting point (distal end) of the target segment. Once the OCT catheter is inserted, the subject is enrolled in the study. With the device energized, the OCT catheter will be retracted through the exact same target segment of the vessel and the OCT images captured on the Lightbox system.

The diameter of the lumen of the vessel at the starting, mid, and ending points of the target segment will be measured using the OCT system software. Mean diameter and luminal area will be calculated for each target segment imaged.

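### Criterion 4 removes IVUS adverse events recognised by IVUS removal from the enrolled set, and subjects exit before the OCT catheter is removed; both can raise the overall event-free rate, and the first also tilts the device comparison against OCT

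*Combined protocol and SAP*

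**What the plan says.** **Entry.** Criterion 4 in Section 5.1 reads "Successful diagnostic imaging and removal of the IVUS catheter with no adverse events". Section 5.4 states: "Subjects will be considered enrolled into the study once the consent form is signed and the Pantheris catheter is introduced into the vasculature". Section 6.1 agrees: "Once the OCT catheter is inserted, the subject is enrolled in the study". Section 6.1 also puts IVUS first, with its catheter taken out before the OCT catheter is advanced. Consent comes earlier: "After providing informed consent, the subject will be prepared for the diagnostic procedure".

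**Exit.** Section 5.4 states: "Subjects will be considered exited from the study once the Pantheris catheter (OCT device) diagnostic imaging and vessel measurements have been completed". Section 6.1 adds that removing the OCT catheter, or using it for atherectomy, is a choice made after exit. Section 5.5 says "Participation lasts the duration of the diagnostic imaging procedure" and "No follow-up imaging or patient data will be collected".

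**Endpoint and analysis.** The primary safety endpoint in Section 5.3 is freedom from adverse events related to the imaging procedure or associated with the device, as the physician reports them. It names neither device and gives no time window. Section 6.3 plans a matched-pairs t-test that covers complications of the two techniques, and separately names Fisher's exact test for proportions. Section 7.1 has events assessed after each scan and requires serious events to be reported whether or not they are thought related, with no stated end time.

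**The concern.** There are two separate defects.

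(a) One arm of the paired comparison is selected on its own outcome. A patient with an IVUS event known by the time the IVUS catheter is out is not eligible, so does not contribute to the enrolled set. A report of no IVUS events in 25 subjects would restate an entry condition, yet could be read as evidence on IVUS safety. The same selection reaches the primary safety endpoint, because Section 5.3 covers the imaging procedure and the devices in general, and both catheters are study devices (Section 2).

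(b) The devices are observed to different points. IVUS is judged through catheter removal; OCT is observed only to the end of imaging and measurement. The OCT pullback through the target segment is inside the window, but final removal is not. Section 3.1 lists vessel spasm, dissection and bleeding among the risks of these catheters, and nothing in the plan suggests that such events stop when imaging stops.

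At stake are the primary safety result and any statement that compares the complications of the two devices.

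**Working it through.** **The plan's own figure.** There is none to reproduce for safety: the documents give no adverse event rate, safety margin or safety sample size. Only n = 25 (Sections 5.1 and 5.2) comes from the documents. The rest is assumed: true risk r of 2% to 5%, equal for the two devices and independent between them. Section 6.3 gives p < 0.05 without sidedness, so both versions are shown.

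**Step 1: what the paired test can return.** With IVUS at 0, each subject's difference (OCT minus IVUS) is 1 or 0. For x OCT events in 25, the mean is x/25, the SD is √[x(25−x)/(25×24)], and t = mean/(SD/5) on 24 df.

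| OCT events | Mean | SD | t | Two-sided p | One-sided p |
|---|---|---|---|---|---|
| 0 | 0 | 0 | undefined | – | – |
| 3 | 0.12 | 0.332 | 1.809 | 0.083 | 0.041 |
| 4 | 0.16 | 0.374 | 2.138 | 0.043 | 0.021 |

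The mean cannot be negative. Fisher's test does not change this. It needs 6 OCT events against 0 (two-sided p = 0.022; 5 events give p = 0.0502), and the IVUS count is still set by eligibility.

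**Step 2: chance of a false 'OCT worse'.** With X ~ Binomial(25, r):
- Two-sided 0.05, P(X ≥ 4): 0.14% at r = 2%, 3.4% at r = 5%. Without the selection, exact enumeration gives 0.09% and 1.0% in each direction.
- One-sided 0.05, P(X ≥ 3): 1.3% and 12.7%.
- Undefined t statistic, P(X = 0): 0.98^25 = 60% and 0.95^25 = 28%.

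**Step 3: IVUS events left out.** The expected number of patients with an IVUS event before the 25th enrolment is 25r/(1−r): 0.5/0.98 = 0.51 and 1.25/0.95 = 1.32. The chance of at least one is 1−(1−r)^25: 40% and 72%.

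**Step 4: effect of (a) on the primary safety endpoint.** Counting everyone from IVUS insertion, with both devices' events included, the event-free rate is (1−r)²: 96.0% at 2%, 90.3% at 5%. In enrolled subjects it is 1−r: 98% and 95%. The difference, r(1−r), is 2.0 and 4.8 points. This ignores patients whose IVUS imaging was unsuccessful but event-free.

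**Step 5: effect of (b).** If a share f of OCT events arises at or after exit, the event-free rate is overstated by r×f. The documents give no basis for any value of f.

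| f (assumed) | r = 2% | r = 5% |
|---|---|---|
| 10% | 0.2 points | 0.5 points |
| 50% | 1.0 point | 2.5 points |

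**The case against.** **On (a).** A reader might infer that an IVUS event can never be counted in an enrolled subject. The documents do not go that far. Criterion 4 screens on what is known by IVUS removal. An IVUS injury first recognised later, for example at the assessment after the OCT scan, could still be attributed to IVUS. The assessment after each scan makes this unlikely, and there is no attribution rule, so the zero holds for events recognised by IVUS removal and no further.

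It is also fair to say that the test was weak in any case. Without the selection it would find 'IVUS worse' in only 0.09% to 1.0% of trials, and the comparison is not an endpoint in Section 5.3. That stands. The larger harm is an IVUS count without information, and its effect on the primary safety endpoint. The independence assumption also matters: if the same patients are vulnerable to both catheters, criterion 4 lowers OCT risk among those enrolled, and Step 2 overstates the false 'OCT worse' rate.

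Section 5.4 already records reasons for premature termination and requires an adverse event form where an event is the cause. It does not say whether this reaches consented patients who are not yet enrolled.

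**On (b).** A reader might infer that the plan expressly excludes removal events from the primary endpoint. It does not. Section 5.3 has no window, the phrase in Section 5.5 about the duration of the procedure could be read to include removal, and Section 7.1 could bring in a serious event after exit. What stands is that Sections 5.4 and 6.1 place exit before removal, Section 5.5 collects nothing later, and no section places removal events in the endpoint.

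**On both together.** A reader might also infer that the two defects offset each other, since one works against OCT and the other in its favour. That is true only of the device comparison, where nothing makes them cancel. For the overall event-free rate both push upward.

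**Conclusion.** Both defects follow from the text and should be fixed. The qualitative result needs no assumed rate: IVUS events recognised by IVUS removal are zero by rule among enrolled subjects, the paired comparison can in practice go only against OCT or show nothing, and events at OCT removal have no stated place in the endpoint.

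The sizes are modest and rest wholly on assumptions: 25 subjects, equal and independent risks of 2% to 5%, and an arbitrary share of events after exit. On those terms a false 'OCT worse' finding is uncommon with a two-sided test and reaches 12.7% only with a one-sided test at 5% risk. The overall event-free rate would be raised by about 2.0 to 4.8 points through (a) if both devices' events count, and by 0.2 to 2.5 points through (b). The documents do not support a claim of large distortion. They do support the conclusion that the safety results, as planned, cannot be read at face value.

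**What to change.** 1. Keep criterion 4. Define the safety set as all consented subjects from IVUS catheter insertion and compute the Section 5.3 safety endpoint in that set. Record whether each proceeded to OCT and, if not, why. Apply the termination reason and adverse event form of Section 5.4 to those who did not.
2. Reconcile Sections 5.3, 5.4, 5.5, 6.1 and 7.1 so that the OCT safety window is stated and includes catheter removal. Where the catheter is kept for atherectomy, count to the start of atherectomy and report those subjects separately, because their window is shorter than the one for IVUS.
3. Replace the paired t-test of complications with each device's event proportion and exact 95% confidence interval, reported descriptively. For example, 1 IVUS event in 26 would be 3.8% (0.1% to 19.6%), and 0 OCT events in 25 would be 0% (0% to 13.7%). State that OCT is observed only in patients who came through IVUS without an event, so the denominators are not alike. Report access-site events once, at procedure level, because a single sheath serves both catheters (Section 6.1: "A 7 Fr vascular sheath will be advanced up-and-over the aortic bifurcation and to the region of interest of the artery").
4. State that late events, such as the infection and renal failure listed in Section 3.1, are not captured.

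**Cost.** A protocol amendment with sponsor agreement and IRB approval (Section 9.3) and a small case report form change. Safety data would be needed on about 0.5 to 1.3 more patients under the assumed risks, plus any whose IVUS imaging was unsuccessful. No procedure, visit or follow-up is added.

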## **5.2. Sample Size Estimate**

When the sample size is 108 images of both the OCT and IVUS catheters, a two group 0.05 one-sided matched t-test will have 90% power to reject the null hypothesis that the test (OCT) and standard (IVUS) are not equivalent in favor of the alternative hypothesis that the two groups are equivalent. To obtain 108 vessel segment images at five images per subject, 22 subjects would be needed; however, recognizing that some images (~ 5%) may be of poor quality and illegible, 25 subjects should be enrolled and 115 images evaluated.

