### 6.3 Statistical Analyses

Statistical analyses will be carried out using StatView software (SAS Institute, Cary, NC). A  $p$  value  $< 0.05$  will be considered statistically significant. Matched Pairs  $t$ -Test will be performed to compare means and on paired samples to compare procedural data and complications associated with the imaging techniques. The mean values of the results of all readings of all readers will be calculated for comparison of image quality. Fisher's Exact Test will be used to compare proportions. The Mann-Whitney-Wilcoxon test will be applied for statistical comparison of the results for OCT and IVUS imaging. Interreader and intrareader reproducibility will be calculated by intraclass correlation (ICC) analysis in a two-way mixed model. Correlation of the mean values of the results of the quantitative measurements of all readers with both imaging modalities will be calculated as Pearson correlation coefficient.

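### The sample size and image-quality tests treat about five images per patient as independent, so the 90% power is not established and the primary comparison's error rate is not controlled

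*Combined protocol and SAP*

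**What the plan says.** Section 5.2 states that with 108 images per device "a two group 0.05 one-sided matched t-test will have 90% power to reject the null hypothesis" of non-equivalence. The patient count follows by division: "To obtain 108 vessel segment images at five images per subject, 22 subjects would be needed". An allowance of about 5% for unreadable images then leads to "25 subjects should be enrolled and 115 images evaluated". The section gives no margin, SD or within-patient correlation.

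Under Section 5.1, "IVUS and OCT images will be captured at identical positions within vessel segments". Section 6.1 describes one target segment per patient and one pullback per device, the IVUS catheter being "retracted through the target segment (between 5 cm and 10 cm within the vessel) capturing images within the target segment".

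Section 6.3 names two tests that could serve the image-quality comparison. The matched-pairs t-test "will be performed to compare means and on paired samples to compare procedural data and complications associated with the imaging techniques". Separately, "The Mann-Whitney-Wilcoxon test will be applied for statistical comparison of the results for OCT and IVUS imaging". Scores are averaged over readings and readers. The only ICC in the plan concerns reader reproducibility. The per-segment means in Section 6.1 cover lumen diameter and area, which belong to the secondary endpoint in Section 5.3.

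**The concern.** About five image pairs from one short segment, taken in the same two pullbacks, are unlikely to carry as much information as five pairs from five patients. Vessel, disease and operator effects common to both devices largely cancel in the OCT minus IVUS difference. The ICC of the differences may therefore be lower than that of the raw scores. Effects that differ by device within a patient do not cancel. The Introduction names one for OCT, where "imaging requires management of blood flow, which can interfere with light transmission", and says that wall calcium limits IVUS penetration. Both can plausibly vary between patients.

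The primary claim is that OCT is equivalent to or better than IVUS. If the paired differences are positively correlated within a patient, an image-level matched test understates the standard error and makes that claim too often when it is false. The Mann-Whitney-Wilcoxon test adds a second mismatch, because it treats matched images as two independent samples.

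**Working it through.** **The plan's own figures.** 108 / 5 = 21.6, hence 22 patients. 108 / 0.95 = 113.7, hence 114 images, close to the stated 115. The patient count is plain division, which assumes independent pairs. The 90% cannot be reproduced without a margin and SD. By the noncentral t distribution (one-sided 0.05), 108 independent pairs give 90% power at a margin of 0.283 SD of the differences.

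**Layout.** The documents give 25 patients and 115 pairs. I assumed 15 patients with 5 pairs and 10 with 4: 15 × 5 + 10 × 4 = 115.

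**Design effect.** DE = 1 + (Σm² / Σm − 1) × ICC. Here Σm² = 15 × 25 + 10 × 16 = 535 and 535 / 115 = 4.652, so DE = 1 + 3.652 × ICC. Effective pairs = 115 / DE.

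**Error of the image-level matched test at the margin, nominal one-sided 5%.** Approximate error = 1 − Φ(1.645 / √DE), checked by 60,000 simulated trials per ICC with normal differences.

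| ICC of differences (assumed) | DE | Effective pairs | Error, formula | Error, simulated |
|---|---|---|---|---|
| 0 | 1.00 | 115 | 5.0% | 5.0% |
| 0.05 | 1.18 | 97 | 6.5% | 6.6% |
| 0.1 | 1.37 | 84 | 8.0% | 8.0% |
| 0.3 | 2.10 | 55 | 12.8% | 12.6% |
| 0.5 | 2.83 | 41 | 16.4% | 16.6% |

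In the same simulations a one-sample t-test on the 25 patient means kept its error at 4.9% to 5.1%.

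**Error of the unpaired Mann-Whitney-Wilcoxon test.** This also depends on the between-device correlation r at matched positions, which the documents do not give. There were 20,000 simulated trials per cell, with normal scores and r split equally between patient and position effects. Ties were not simulated.

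| ICC | r = 0 | r = 0.5 | r = 0.7 |
|---|---|---|---|
| 0 | 5.0% | 1.1% | 0.2% |
| 0.05 | 5.9% | 1.9% | 0.5% |
| 0.1 | 7.9% | 2.3% | 0.7% |
| 0.3 | 12.6% | 5.8% | 1.9% |
| 0.5 | 16.3% | 8.4% | 3.9% |

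A separate rerun agreed within about one percentage point. Ignoring the pairing pulls the error down and ignoring the clustering pushes it up, so the net direction is unknown.

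**Power of a valid patient-level test.** The variance of the average patient-mean difference, in units of the squared SD of the differences, is [ICC + (1 − ICC) × 0.22] / 25, where 0.22 = (15/5 + 10/4) / 25. Power is noncentral t with 24 df and noncentrality margin / √variance. Example at ICC 0.1 and margin 0.283: variance = (0.1 + 0.9 × 0.22) / 25 = 0.0119, noncentrality = 0.283 / 0.109 = 2.6, power 81%.

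The margin is unknown, so I used three readings. The second and third suppose that 108 per group came from an unpaired formula, which gives 90.06% at 0.40 SD of raw scores. One SD of raw scores equals 1 / √(2(1 − r)) SD of the differences. So 0.40 becomes 0.40 at r = 0.5 and 0.40 / √0.6 = 0.516 at r = 0.7.

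| Margin, SD of differences | ICC 0.1 | ICC 0.3 | ICC 0.5 |
|---|---|---|---|
| 0.283 | 81% | 65% | 55% |
| 0.40 | 97% | 89% | 80% |
| 0.516 | 99.8% | 98% | 94% |

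**The case against.** Five points can fairly be made for the plan.

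- **Unit of analysis.** Section 6.3 never says that the image-quality tests run on images. This stands as a caveat. Still, the 108 and 115 are image counts and no patient-level step appears, so image level is the natural reading. If patient-level analysis was meant, the text must say so, and the image-based power in Section 5.2 would still not match it.
- **Which test.** The matched-test errors may belong to a test not used for the primary comparison, and Mann-Whitney-Wilcoxon can be conservative. This stands in part: at r = 0.7 its error is below 5% at every ICC shown. But r is unknown, and an error that may fall anywhere from 0.2% to 16% is not controlled.
- **Sidedness.** Section 6.3 says only that p below 0.05 is significant. If that is two-sided, the upper-tail error of the matched test is about 2.5%, 3.5%, 4.7%, 8.8% and 12.5% at ICC 0, 0.05, 0.1, 0.3 and 0.5. It stays under 5% up to ICC 0.1, but the nominal 2.5% tail is still inflated.
- **Margin.** Without a margin, the false-claim rate for equivalence is not fully defined, and that gap alone makes the 90% uncheckable. This is correct. Clustering is a separate fault that a stated margin would not remove.
- **Power scenarios.** The 0.40 SD origin is only suggestive, because one free margin can reproduce any sample size. A two-sided equivalence reading loses more: with 22 patients and the margin back-solved for that test (0.32 SD), power is about 75%, 44% and 21% at ICC 0.1, 0.3 and 0.5. This widens the uncertainty but does not support the 90%.

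**Conclusion.** The concern holds. Section 5.2 rests on independence between images of the same patient, and nothing in the documents supports that assumption or corrects for it. For an image-level matched test at one-sided 5%, any positive ICC of the differences raises the error above nominal: about 6.5% to 17% for ICC 0.05 to 0.5, and no inflation at ICC 0. For the Mann-Whitney-Wilcoxon test, the error may be above or below 5%. Patient-level power runs from 55% to above 90% across the scenarios shown, so the documents do not settle on which side of 90% it lies.

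The omission is certain; its size is not. The ICC, r, margin and layout are my assumptions, and normal scores stand in for 3- to 5-point scales. Because the fault lies in the primary efficacy comparison, it should be corrected before analysis.

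**What to change.** **Section 6.3.** Make the primary OCT versus IVUS comparison a one-sided paired test, against a stated margin, on patient-mean differences: average the three readers, then average the differences over each patient's matched positions. Alternatively, fit a mixed model to the image pairs with a random patient effect and small-sample degrees of freedom. Either replaces both the image-level matched t-test and the Mann-Whitney-Wilcoxon test for this comparison. State how a patient with no scorable position on an item, such as bifurcation, is handled.

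**Section 5.2.** Reconcile the two-group and matched descriptions of the test. State the margin and the SD used. Restate power for 25 patients and 115 image pairs over a stated ICC range.

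**Cost.** Two sections are reworded and the same data get a slightly more complex analysis. Enrolment, imaging and reading do not change. If the differences really are uncorrelated, almost nothing is lost: at ICC 0 and a margin of 0.283 SD, the patient-mean test on 115 pairs still has 90% power. Otherwise the stated power may become less favourable.
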